10.6 OPERATIVE PROCEDURES

Surgical procedures should be in accordance with your routine practice and in accordance with the labeling. The surgeons should follow the procedures as described in the DFU for appropriate alignment of the IOL axis.

NOTE: *No additional refractive procedures are to be performed during the operative procedure or throughout the postoperative study period (e.g., LRI, OCCI, CRI, AK, PRK, LASIK or LASEK).*

NOTE: *Optiwave Refractive Analysis (ORA) can be used as a part of routine cataract surgery to improve accuracy of the correction. If ORA is used it will be documented in the Operative case report form.*

The Operative case report forms may include the following information:

INCISION TYPE AND SIZE

The incision may be clear corneal, limbal or scleral tunnel at the discretion of the investigator. Lenses should be inserted per the investigator's standard technique when using the JJSV-qualified implantation system.

CAPSULORHEXIS SIZE AND METHOD

The anterior capsulotomy should be made per the investigator's standard technique. The anterior capsulotomy method may be manual or laser-assisted.

LENS REMOVAL

Lens removal may be performed using phacoemulsification/aspiration only, or through laser-assisted fragmentation and phacoemulsification/aspiration.

OPHTHALMIC VISCO SURGICAL DEVICE (OVD)

OVD materials should be used as is customary for each investigator

IMPLANT INSTRUMENTATION USED

Lenses should be folded for implantation and inserted into the capsular bag using the JJSV-qualified implantation system. **NOTE:** *Capsular tension ring can be used per surgeon discretion.*

SURGICAL COMPLICATIONS

Should a surgical complication occur, implantation of a study lens will be at the investigator's discretion. However, in the event of capsular bag or zonular rupture, the study lens should not be implanted. Additionally, the lens is not to be implanted in the sulcus. In this case, the investigator may implant his/her choice of an alternative backup IOL.

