- Visual symptoms requiring secondary surgical intervention (e.g., lens removal)
- Tilt, decentration, IOL rotation requiring secondary surgical intervention (e.g., repositioning)
- Residual refractive error resulting in a secondary surgical intervention
- Retained lens material resulting in secondary surgical intervention

NOTE 1: *Wound burps during the first week postoperatively, suture removal, planned blepharoplasty and Nd:YAG capsulotomy (for PCO) are not considered adverse events for this study.*

NOTE 2: *Corneal edema, and chronic anterior uveitis/iritis will be considered serious if corneal edema resulting in BCDVA of 20/40 or worse at 1 month or later; and Grade 1+ uveitis/iritis persists for greater than 3 months after surgery). Raised IOP requiring treatment (Elevation of IOP \geq 10 mmHg above baseline to a minimum of 25 mmHg) will be considered serious if present at the last study visit.*

Unanticipated Adverse Device Effect (UADE)/Unanticipated Serious Adverse Device Effect (USADE)

Any USADE (ISO 14155) is defined as any serious adverse effect on health or safety or any life-threatening problem or death caused by, or associated with, a device, if that effect, problem, or death was not previously identified in nature, severity, or degree of incidence in the investigational plan (i.e., this protocol), application (including a supplementary plan or application), or risk assessment, or any other unanticipated serious problem associated with a device that relates to the rights, safety, or welfare of subjects.

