20. STATISTICAL METHODS

This section highlights the analyses to be performed for key study endpoints. The 3-month postoperative visit is the critical analysis time point for the primary endpoint and for other data from the SSQ questionnaire, the SEQ questionnaire and for refraction and visual acuity endpoints. The operative visit is the key timepoint for evaluation of data from the SHQ questionnaire. The one-week visit is the key timepoint for the SSQ question on rotational stability.

Descriptive statistics will typically include mean, standard deviation, median, minimum, maximum for continuous data with frequency and proportion reported for categorical data.

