20.1 ANALYSIS POPULATION

For the primary endpoint, the primary analysis population will be all eyes implanted with a toric IOL (model ZCU150 through ZCU600) and with available data at the 3-month visit. For other endpoints, all eyes implanted with a toric IOL model ZCU150 to ZCU600 and with available data at the key timepoint for that endpoint will be used. In addition, data for the primary endpoint will also be evaluated by IOL model for lower-cylinder IOLs (ZCU150), medium-cylinder IOLs (ZCU225 to ZCU375) and for extended higher-cylinder IOLs (ZCU450, ZCU525 and ZCU600). For the surgeon preference questionnaire (SPQ) and the surgeon experience questionnaire (SEQ), the analysis population will be surgeons responding to these questionnaires.

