20.2 PRIMARY ENDPOINT

The primary endpoint for this study is the response to a single-item evaluating the surgeon's rating of overall level of satisfaction with the clinical outcome for each eye from the SSQ. Surgeon satisfaction is defined as having a score of 4 (satisfied) or 5 (very satisfied). The frequency and proportion of eyes with a rating of 4 or 5 and the 95% confidence interval for this proportion will be reported. In addition, the frequency and proportion with each response will be tabulated for this item.

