20.4 SAMPLE SIZE CALCULATIONS

With a minimum of 1000 eyes, the two-sided 95% confidence interval for the proportion of eyes rated as having acceptable performance will extend within 1.4% from the observed proportion assuming an expected overall satisfactory proportion of 95%.

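### Sections 20.1 to 20.3 have no rule for eyes that have IOL repositioning, lens exchange or another secondary refractive intervention before the 3-month visit, and neither path open to such an eye counts it as a failure

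*Combined protocol and SAP*

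**What the plan says.** - **Population (section 20.1).** The primary analysis uses "all eyes implanted with a toric IOL (model ZCU150 through ZCU600) and with available data at the 3-month visit". For the other endpoints, implanted eyes "with available data at the key timepoint for that endpoint will be used".
- **Endpoints (sections 20.2 and 20.3).** A 3-month score of 4 or 5 on SSQ item 1 is a success. Refraction and acuity are summarised for all eyes. No condition refers to a secondary intervention.
- **Foreseen events (section 11.1).** The anticipated serious events include "Tilt, decentration, IOL rotation requiring secondary surgical intervention (e.g., repositioning" and "Residual refractive error resulting in a secondary surgical intervention".
- **Follow-up (section 10.8).** A subject with at least one study lens is followed per protocol. Discontinuation is compulsory on death, or on lens removal when the fellow eye has no study lens. After a lens removal or other serious adverse event, exit is optional.
- **Timing (sections 20 and 10.7).** "The one-week visit is the key timepoint for the SSQ question on rotational stability", but the full three-item SSQ, including rotational stability, is also collected at 3 months.
- **Refractive procedures (section 10.6).** "No additional refractive procedures are to be performed during the operative procedure or throughout the postoperative study period".
- **Separate reporting (section 6.2, item 7).** Secondary surgical interventions are tabulated by eye.

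**The concern.** The lens is presented as designed to limit rotation (sections 2 and 7.1). Appendix A schedules no measurement of lens axis, so the planned evidence on stability is the surgeon's rating, supported by refraction, acuity and event counts.

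Take a lens that rotates, is surgically repositioned, and is well aligned at month 3. The surgeon may fairly rate that eye 4 or 5, and its cylinder may lie within 0.50 D of intended. Under section 20.1 the eye then enters the primary proportion and the refractive results as a success of the implanted lens. The need for a second operation appears only in a separate table, which does not show how many of the reported successes had one. If the subject is exited instead, the eye has no 3-month rating and drops out of the denominator. The plan does not say which will happen.

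At stake is a modest favourable shift in satisfaction, 3-month stability, UCDVA, cylinder, spherical equivalent and percent reduction in cylinder.

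**Working it through.** **1. The plan's own figure.** Section 20.4 states that "the two-sided 95% confidence interval for the proportion of eyes rated as having acceptable performance will extend within 1.4% from the observed proportion", with 1000 eyes and an expected 95%. The usual normal-approximation half-width, with eyes treated as independent, is

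1.96 × √(0.95 × 0.05 / 1000) = 0.0135, or 1.35 points.

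This reproduces the stated 1.4%. The figure is not in dispute; it serves below as a yardstick.

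**2. Eye followed after the intervention.** Let r be the share of analysed eyes with an intervention before the 3-month rating, and s the share of those rated 4 or 5. Counting them as not satisfied changes the proportion from p to p − r × s. The documents give neither r nor s, so both are assumptions. With p = 95% and n = 1000:

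| r | s = 1 (upper bound) | 95% CI | s = 0.5 | 95% CI |
|---|---|---|---|---|
| 1% | 94.0% | 92.5 to 95.5 | 94.5% | 93.1 to 95.9 |
| 2% | 93.0% | 91.4 to 94.6 | 94.0% | 92.5 to 95.5 |
| 3% | 92.0% | 90.3 to 93.7 | 93.5% | 92.0 to 95.0 |

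The shift equals the planned half-width when r × s = 1.35%. That means r = 1.35% if every such eye is rated satisfied, and r = 1.35 / 0.5 = 2.7% if half are.

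**3. Subject exited after the intervention.** Of 1000 implanted eyes, suppose a share r leaves and 95% of the rest are rated 4 or 5. The plan reports 95%. With the exited eyes restored as failures the figure is 0.95 × (1 − r): 94.05%, 93.1% and 92.15% for r of 1%, 2% and 3%. The effect is of similar size by either path.

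**4. Direction.** For the proportions, counting these eyes as failures can lower the result or leave it unchanged; it cannot raise it. For mean refraction and acuity a favourable shift is to be expected, because the intervention aims to improve them, but it does not follow by arithmetic.

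**5. Cylinder groups.** Section 20.1 also reports the primary endpoint by cylinder group, with no stated group sizes. In an assumed group of 50 eyes, one affected eye moves the result by 1/50 = 2 points.

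**6. Which endpoints are exposed.**
- Exposed: SSQ items 1, 2 and 3 at 3 months, UCDVA and BCDVA, cylinder, spherical equivalent, percent reduction.
- Exposed only if the intervention comes before the visit at days 5 to 14: the 1-week stability rating, which is the key one.
- Not affected: the SHQ, completed at surgery, and the SEQ, answered once per surgeon.

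**The case against.** The primary endpoint is a surgeon's opinion of the outcome achieved in the eye. Surgeons know about a reoperation and can mark the eye down for it. Reporting outcomes whatever happened in between is a legitimate choice, and recoding a 4 or 5 as not satisfied creates a composite endpoint. The plan has no threshold or hypothesis test, so no decision would be reversed. This stands. It is why the as-rated result should remain and the recoded one be supplementary; it is no reason to leave the handling unstated.

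Three stronger readings are tempting, and the documents do not support them:

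- *Such eyes remain in every analysis.* The SHQ and SEQ are not affected, the key stability rating is usually made early, and optional exit means that retention is not assured.
- *The interventions are concealed.* Section 6.2 reports them. The gap is that this count is not linked to the satisfaction and refractive figures.
- *Sections 10.6 and 11.1 set contradictory treatment rules.* Section 11.1 lists events to report if they occur and does not authorise a procedure. The examples in section 10.6 are incisional and laser corneal procedures, while a secondary intervention in section 11.1 could be repositioning or lens removal. The two passages still need to be reconciled, because a reader cannot tell how they fit together or what an intervention of this kind means for the analysis.

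**Conclusion.** The concern holds as a gap in the analysis rules. An eye that needed a second intervention on the lens or refraction before month 3 is either reported with its post-intervention result or absent, and in neither case is it counted as a failure. For the proportions, any resulting bias favours the lens.

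The size cannot be fixed from the documents. On assumed rates of 1% to 3%, the primary proportion would be 1 to 3 points lower if every affected eye is rated satisfied, and 0.5 to 1.5 points lower if half are. Only when r × s is above about 1.35% does the shift pass the planned precision.

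A reader might infer from the 2% row, with its upper limit of 94.6%, that the data would exclude the reported 95%. That does not follow: the two figures are different definitions applied to the same eyes, not independent estimates. Nor do the documents give grounds for resting the study's conclusion on the lower figure.

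**What to change.** 1. **Section 20.2.** Keep the as-rated analysis. Add one pre-specified supplementary row, with its 95% CI, in which any eye with a secondary intervention on the lens or refraction before its 3-month rating counts as not satisfied. Include eyes exited for that reason in its denominator. State the number of such eyes overall and by cylinder group.
2. **Section 20.3.** Add the same row for the 3-month SSQ item 2 and for the proportions within 0.50 D and 1.00 D of intended. Show mean refraction and acuity with and without these eyes, using pre-intervention values where the Unscheduled Visit CRF already holds them. Section 10.9 leaves those measurements to the investigator's discretion, so some will be missing.
3. **Interpretation.** Read the as-rated result alongside the supplementary row.
4. **Sections 10.6 and 11.1.** Reconcile the two passages and state the analysis consequence of an intervention.

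The cost is some SAP wording and a little extra tabulation, with no new data collection. The downside is a supplementary figure that may be slightly less favourable.

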20.2 PRIMARY ENDPOINT

The primary endpoint for this study is the response to a single-item evaluating the surgeon's rating of overall level of satisfaction with the clinical outcome for each eye from the SSQ. Surgeon satisfaction is defined as having a score of 4 (satisfied) or 5 (very satisfied). The frequency and proportion of eyes with a rating of 4 or 5 and the 95% confidence interval for this proportion will be reported. In addition, the frequency and proportion with each response will be tabulated for this item.

20.3 OTHER ENDPOINTS

For other items on the SSQ, the frequency and proportion of eyes with each response will be reported for the individual items on the questionnaire. The frequency and proportion of eyes will be reported for the single-item on the SHQ. For the SEQ and the SPQ, the frequency and proportion of surgeons with each response will be reported.

Descriptive statistics for all eyes will be reported for mean refractive cylinder, cylinder vs intended cylinder, spherical equivalent and spherical equivalent vs intended and for percent reduction in cylinder. In addition, the frequency and proportion of eyes within 0.50 D and within 1.00 D of intended values will be reported for refractive cylinder and spherical equivalent.

For visual acuity, the values will be converted to logMAR prior to analysis. Descriptive statistics for all eyes will be reported for mean logMAR monocular uncorrected and best corrected distance visual acuity. The frequency and proportion of eyes achieving each acuity line will also be reported for uncorrected and best corrected distance visual acuity.

Enrollment data, demographic data, accountability data and operative complications/procedures will be reported using descriptive statistics.

The frequency and proportion of eyes with medical/lens findings or adverse events will also be reported.

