1. SYNOPSIS

PROTOCOL: Post-market Evaluation of Surgeon Feedback on TECNIS® TORIC II Intraocular Lens (IOL)

Protocol Number: NXGT-201-TTL2

STUDY LENS: TECNIS® TORIC II - One-Piece Aspheric Acrylic Monofocal Posterior Chamber IOL (Model ZCU)

STUDY OBJECTIVE: The purpose of this post-market clinical study is to obtain surgeon feedback on the clinical outcomes achieved in the eyes implanted with the TECNIS Toric II IOL.

CLINICAL HYPOTHESIS: The overall clinical outcomes of eyes implanted with the TECNIS Toric II IOL will be satisfactory to the surgeons.

STUDY ENDPOINTS: **Primary Endpoint**

Overall surgeon satisfaction of the clinical outcomes assessed by a single-item on the Surgeon Satisfaction Questionnaire (SSQ) for each eye implanted with the study lens at the 3-month postoperative visit.

The percentage of eyes with overall surgeon satisfaction being satisfied or very satisfied (defined by a score of 4 or 5) will be calculated.

Other Endpoints

1. Surgeon responses for a single-item in the Surgical Handleability Questionnaire (SHQ)
2. Surgeon responses for additional items in the Surgeon Satisfaction Questionnaire (SSQ)
3. Surgeon responses for items in the Surgeon Overall Experience Questionnaire (SEQ)
4. The manifest refractive cylinder and spherical equivalent as compared to intended
5. Percent reduction in cylinder
6. Uncorrected and best corrected distance visual acuities
7. Medical findings/lens findings/complications/adverse events

OVERALL STUDY DESIGN:

Structure: Prospective, multicenter, single-arm, open-label

Number of sites: Up to 50 sites in the United States

Duration: Three months

Indication: The TECNIS® Toric II 1-Piece posterior chamber lenses are indicated for the visual correction of aphakia and pre-existing corneal astigmatism of one diopter or greater in adult patients with or without presbyopia in whom a cataractous lens has been removed by phacoemulsification and who desire improved uncorrected distance vision, reduction in residual refractive cylinder, and increased spectacle independence for distance vision. The device is intended to be placed in the capsular bag.

Administration: Refractive target outcomes will be emmetropia for each eye. Surgeons will perform standardized, small-incision, cataract surgery and implant the study lenses using a JJSV-validated insertion system qualified for use with TECNIS Toric II lenses as specified in the Directions for Use (DFU).

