Visit Schedule: Subjects will be implanted with the TECNIS Toric II IOL in one or both eyes qualified for study inclusion. Each eye will undergo four visits: Preoperative; Operative; 1-week; and 3-months.

STUDY POPULATION CHARACTERISTICS:

Condition: Unilateral or bilateral cataract with corneal astigmatism of approximately 1.0 to 6.0 D.

Models ZCU 1.50, 2.25, 3.00, 3.75, 4.50, 5.25, 6.00

Number of Subjects Up to 1100 subjects enrolled with 1,000 subjects treated (unilateral or bilateral treatment)

Inclusion Criteria:

1. Minimum 22 years of age;
2. Unilateral or bilateral cataracts for which phacoemulsification extraction and posterior chamber IOL implantation have been planned;
3. Corneal astigmatism of one diopter or more in the operative eye;
4. Potential for postoperative best corrected distance visual acuity (BCDVA) of 20/30 Snellen or better;
5. Clear intraocular media other than cataract in each eye;
6. Ability to understand, read and write English in order to consent to study participation;
7. Availability, willingness, sufficient cognitive awareness to comply with examination procedures;
8. Signed Informed Consent Document (ICD) and Health Insurance Portability and Accountability Act (HIPAA) authorization.

Exclusion Criteria:

1. Recurrent severe anterior or posterior segment inflammation or uveitis;
2. Compromised eye due to previous trauma or developmental defects in which appropriate support of the IOL is not possible;
3. Circumstances that would result in damage to the endothelium during implantation;
4. Suspected ocular microbial infection;
5. Subjects with conditions associated with increased risk of zonular rupture, including capsular or zonular abnormalities that may lead to IOL decentration, including pseudoexfoliation, trauma, or posterior capsule defects;
6. Known ocular disease or pathology that, in the opinion of the investigator, may affect visual acuity or require surgical intervention during the course of the study, [macular degeneration, cystoid macular edema, proliferative diabetic retinopathy (severe), uncontrolled glaucoma, irregular corneal astigmatism, choroidal hemorrhage, concomitant severe eye disease, extremely shallow anterior chamber, microphthalmos, non-age related cataract, severe corneal dystrophy, severe optic nerve atrophy, etc.];
7. Planned monovision correction (eye designated for near vision correction);

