7. STUDY PRODUCTS

7.1 INTRAOCCULAR LENS

The TECNIS Toric II IOL (study lens), Models ZCU150, ZCU225, ZCU300, ZCU375, ZCU450, ZCU525, and ZCU600 are posterior chamber, 1-piece, aspheric, hydrophobic acrylic foldable IOLs and are to be implanted in the capsular bag following cataract extraction. It is designed to minimize the occurrence of large rotations (greater than 10°) following implantation.

The TECNIS Toric II is a UV light-absorbing posterior chamber lens that compensates for corneal spherical aberrations and corneal astigmatism. The benefits of aspheric compensation for corneal spherical aberrations are contingent upon full correction of spherical (defocus) and cylindrical (astigmatic) refractive error.

The TECNIS Toric II incorporates an aspheric optic with a squared posterior optic edge designed to provide a 360° barrier for reducing the incidence of posterior capsular opacification (PCO). The visual benefits of the proprietary wavefront-designed aspheric optic have been clinically assessed using the TECNIS® Z9000 IOL (under Investigational Device Exemption G960221). As featured in the currently marketed TECNIS Toric (ZCT Series) design, the edge of the optic is frosted to reduce potential for edge glare effects.

The TECNIS Toric II IOLs have two sets of four axis orientation marks 180° apart in the outer periphery of the anterior optic surface to indicate the meridian of the lowest power (flat meridian). These axis orientation marks are for proper alignment of the flat meridian of the IOL with the steep meridian of the corneal curvature.

The ZCU150, ZCU225, ZCU300, ZCU375, ZCU450, ZCU525, and ZCU600 lens models are intended for cataract patients with pre-existing corneal astigmatism that, when taking surgically

induced astigmatism into account, have approximately 0.75 D to 4.75 D of predicted corneal astigmatism to be corrected (**Table 1**).

TABLE 1
TECNIS Toric II Models ZCU, IOL Astigmatism Correction Range

ZCU IOL Model	Cylinder Power (D)		Correction Range based on combined corneal astigmatism (Preoperative Kcyl ^a + SIA ^b)
	IOL Plane	Corneal Plane	
ZCU150	1.50 D	1.03 D	0.75 – 1.50 D
ZCU225	2.25 D	1.54 D	1.50 – 2.00 D
ZCU300	3.00 D	2.06 D	2.00 – 2.50 D
ZCU375	3.75 D	2.57 D	2.50 – 3.00 D
ZCU450	4.50 D	3.08 D	3.00 – 3.50 D
ZCU525	5.25 D	3.60 D	3.50 – 4.00 D
ZCU600	6.00 D	4.11 D	4.00 – 4.75 D

^aKeratometric cylinder, ^bSurgically induced astigmatism

Table 2 lists the general design characteristics of the TECNIS Toric II IOLs.

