Keratometry, axial length and anterior chamber depth (ACD) must be measured to determine the appropriate lens power for implantation. Optical biometry methods (i.e., IOLMaster®, LENSTAR®) are preferred; however, surgeons should use the biometry method that they have the most experience with. The lens power should be calculated to achieve emmetropia at distance. The IOL power A-constant used for the TECNIS Toric II is 119.3. The physician should determine preoperatively the spherical equivalent and cylindrical power of the lens to be implanted.

NOTE: Surgeon may choose to use 119.3 or personalized A-constant

SURGICAL PREFERENCE QUESTIONNAIRE (SPQ)

Each surgeon will complete a 4-item questionnaire at study start (prior to first subject implantation). The questionnaire will collect information regarding the surgeons' preferred toric IOL (monofocal and presbyopia-correcting) and their average implantation volumes on a monthly basis.

Additional preoperative information may be collected (for each eye included in the study):

- Informed consent documentation
- Subject demographic information
- Planned surgery date(s)
- Ocular history, including presence of ocular pathology

- Any significant medical findings from a slit-lamp exam, dilated fundus exam, intraocular pressure or other.

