10.5 SELECTION OF THE IOL

In order to facilitate IOL selection and axis placement, JJSV provides a web-based proprietary tool, the TECNIS Toric Calculator (www.TecnisToricCalc.com) for the surgeon. Preoperative keratometry and biometry data, incision location, spherical equivalent IOL power, and the surgeon's estimated surgically induced corneal astigmatism are used as inputs for the TECNIS Toric Calculator. These inputs are used to determine the axis of placement in the eye and the predicted residual refractive astigmatism for TECNIS Toric II 1-Piece IOL models.

NOTE: *The TECNIS Toric Calculator also provides an option for including the Posterior Corneal Astigmatism (PCA) (where available). The predetermined value for posterior corneal astigmatism can be included in the calculation by checking the box labeled "Include Posterior Corneal Astigmatism (PCA)".*

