If a subject with one qualifying eye does not receive the study lens due to a surgical complication, the subject may be discontinued from the study after resolution of the complication to ensure safety. Study-specific postoperative data from this subject will not be collected. If the subject has already received a study lens in the first eye, and the second eye does not receive a study lens, the subject's first eye will be followed per the protocol and the second eye will be followed to ensure safety, but data will not be reported for that eye. Thus, in this case, study-specific postoperative data for the first eye will be collected and study-specific postoperative data for the second eye will not be collected.

MEDICATIONS

Preoperative, operative and intraoperative medications should be used as is customary for each investigator and recorded in the source document for each subject, as appropriate. Only medications required for treatment of an SAE will be recorded on the case report forms.

TYPE OF CLOSURE

Wound closure is left to the surgeon's discretion and will be recorded on the case report form.

SURGICAL HANDLEABILITY QUESTIONNAIRE (SHQ)

The surgeon will complete a single-item questionnaire at the operative visit for each implanted eye. The single-item questionnaire will assess surgeon feedback on the handleability of the study lens.

Additional operative information collected may include:

- Date of surgery
- Operative eye
- Lens power and serial number
- Intended spherical equivalent
- Intended cylinder
- Capsular bag polishing
- Lens placement
- Other surgical procedures

- Difficulty of lens implantation
- Serious and/or device-related adverse events
- JJSV product complaints

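### Does Section 20.3 leave open whether intended cylinder means 0 D or the value planned for each eye?

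*Combined protocol and SAP*

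**What the plan says.** Section 20.3 reports descriptive statistics for "mean refractive cylinder, cylinder vs intended cylinder" and the matching pair for spherical equivalent. It adds that "the frequency and proportion of eyes within 0.50 D and within 1.00 D of intended values will be reported for refractive cylinder and spherical equivalent". The synopsis and Section 6.2 carry the same endpoint. None of these places says where the intended cylinder comes from.

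Other sections bear on it:

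- Synopsis, Administration: "Refractive target outcomes will be emmetropia for each eye".
- Section 10.3, on lens power: "The lens power should be calculated to achieve emmetropia at distance".
- Section 10.5, on the toric calculator: "These inputs are used to determine the axis of placement in the eye and the predicted residual refractive astigmatism".
- Section 10.6 lists "Intended cylinder" among the operative items, directly after the intended spherical equivalent. The list is introduced as information that may be collected.

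On the range of astigmatism, the synopsis gives "Unilateral or bilateral cataract with corneal astigmatism of approximately 1.0 to 6.0 D", while Section 7.1 says the lens models are for patients who "have approximately 0.75 D to 4.75 D of predicted corneal astigmatism to be corrected".

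**The concern.** Emmetropia, taken as a complete refractive target, means 0 D of cylinder. The calculator output and the Section 10.6 item point instead to a planned value for each eye, and toric lenses come in fixed steps, so that value is usually not zero. An eye can land close to its plan and still have more than 0.50 D of cylinder.

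If the text truly supported both references, two analysts could follow it and report different rates for the same eyes. In an open-label, single-arm study the choice could also be made after the data were seen. A reader of the report might not know whether the row means a small residual cylinder or closeness to a non-zero plan. The wider range in the synopsis seems to sharpen this: an eye with 6.0 D of corneal astigmatism would have a large planned residual even after perfect surgery.

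**Working it through.** The plan states no figure for this endpoint, so there is none to reproduce. The check has two parts: whether the choice of reference can matter, and which reference the text supports.

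**Planned residual, from Table 1.** Let K be combined corneal astigmatism and C the corneal-plane lens cylinder. The planned residual is I = |K − C|, largest at the top of each range:

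| Model | C (D) | Top of range (D) | Largest I (D) |
|---|---|---|---|
| ZCU150 | 1.03 | 1.50 | 0.47 |
| ZCU225 | 1.54 | 2.00 | 0.46 |
| ZCU300 | 2.06 | 2.50 | 0.44 |
| ZCU375 | 2.57 | 3.00 | 0.43 |
| ZCU450 | 3.08 | 3.50 | 0.42 |
| ZCU525 | 3.60 | 4.00 | 0.40 |
| ZCU600 | 4.11 | 4.75 | 0.64 |

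**One eye.** After a rotation t, achieved cylinder is A = √((K − C)² + 4KC sin²t). Take ZCU450 with K = 3.30 D and t = 5 degrees, the upper end of the design aim in Section 2.

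- A = √(0.22² + 4 × 3.30 × 3.08 × 0.0076) = √(0.0484 + 0.3088) = 0.60 D.
- Distance from plan: 0.60 − 0.22 = 0.38 D, within 0.50 D.
- Distance from 0 D: 0.60 D, not within 0.50 D.

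So the choice of reference can matter.

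**No error.** When A = I, every eye is on plan. The 0 D reading fails only where I exceeds 0.50 D, that is, ZCU600 with K above 4.61 D. This is (4.75 − 4.61)/0.75 = 19% of that model's range. The other six models show no disagreement.

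**Across eyes.** This step needs assumptions that the documents do not supply: a lens mix of 40/25/15/10/5/3/2% from ZCU150 to ZCU600, astigmatism uniform within each range, and ZCU150 limited to 1.00 D or more. Magnitudes are compared. Error is either the same rotation in every eye or random. The random cases use 1,000,000 simulated eyes each.

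| Assumed error | Within 0.50 D of plan | Within 0.50 D of 0 D |
|---|---|---|
| None | 100% | 99.6% |
| Every eye rotated 2.5 degrees | 100% | 98.9% |
| Every eye rotated 5 degrees | 96.6% | 76.9% |
| Random rotation, SD 3 degrees | 98.8% | 93.7% |
| Random rotation, SD 5 degrees | 93.6% | 81.2% |
| Random error, SD 0.20 D per component | 98.3% | 82.1% |
| Random error, SD 0.40 D per component | 71.9% | 47.9% |

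The gap runs from 0.4 points (100 − 99.6) to 24 points (71.9 − 47.9). Its size is set by the assumed error.

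**Which reference the text supports.**

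1. Section 20.3 speaks of intended cylinder and intended spherical equivalent. Section 10.6 lists those same two quantities side by side for each operated eye.
2. If intended were 0 D in every eye, cylinder minus intended would equal cylinder, and Section 20.3 would report one mean twice under two names. A data field that always held 0 would also serve no purpose.
3. The emmetropia sentences tell the surgeon what to aim for. The one in Section 10.3 concerns lens power. A surgeon can aim for emmetropia and still record the residual that the nearest lens step leaves, which is what the calculator in Section 10.5 predicts.

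All three points favour the per-eye value.

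**The case for a change.** The strongest case is that the per-eye reading still leaves details open. Section 10.6 says only that the item may be collected. The calculator is offered rather than required, its posterior-cornea term is optional (Section 10.5), and intraoperative aberrometry is allowed (Section 10.6). The source of the intended value could therefore differ between sites. Section 20.3 does not say whether magnitudes or vectors are compared, or what happens when the value is missing.

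Those gaps are real, but ordinary practice fills them. Both intended values sit in the same optional list, and Section 20.3 cannot be carried out without them, so the planned analysis itself implies that they are recorded. Section 20.1 already restricts each endpoint to eyes with available data, and the sensible extension is to count eyes that have both values. The results are mean cylinder, and cylinder within a number of dioptres of intended, which reads naturally as a difference of magnitudes. Variation in how surgeons plan is part of routine use, which this post-market study sets out to observe.

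The mismatch between 6.0 D in the synopsis and 4.75 D in Section 7.1 also stands as wording, and those statements must be reconciled; nothing here says which is right. It is a separate matter of how the population is described. At 6.0 D the planned residual would be 6.00 − 4.11 = 1.89 D, but Section 20.3 does not use that figure and nothing shows that eyes beyond Table 1 would receive the lens.

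**Conclusion.** The concern does not hold as a defect in the plan. The wording supports one reference clearly better than the other: the cylinder recorded as intended for each eye. An analyst who follows the text would use it and obtain a legitimate descriptive rate. What is left is unstated detail about source, magnitude comparison and missing values, which a table footnote would normally carry.

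Table 1 alone shows that the reference can matter, through planned residuals of up to 0.64 D. How much it would move the rate cannot be found from the documents: about 0.4 points with no error, up to 24 points under assumed error SDs, all with an assumed lens mix and uniform astigmatism. The endpoint is one of the other endpoints, with no hypothesis, threshold or success rule. Mean cylinder is reported in any case. The primary endpoint (surgeon satisfaction at 3 months) and the precision statement in Section 20.4 are unaffected.
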